	Disease response (bone marrow assessment, hematology) will be assessed locally at any time as clinically indicated.						
Pharmacokinetic assessments	Pharmacokinetic (PK) samples will be obtained and evaluated in all participants.						
Key safety	Acute graft-versus-host disease.						
assessments	Chronic graft-versus host disease.						
	Immune-mediated adverse events.						
	Incidence and severity of adverse events and serious adverse events.						
	Changes in vital signs.						
	Changes in laboratory values.						
Other assessments	Biomarker Assessments:						
assessments	Bone marrow aspirate, peripheral blood and plasma samples will be collected for biomarker assays. These include MRD measurements by multiparameter flow cytometry;						
	Samples will be collected at baseline and at regular intervals during the course of the study as defined in the schedule of assessments.						

Data analysis	For adults participants included in the Safety Run-in part of the study, and for the adolescent cohort, the assessment of the acceptable level of toxicity with sabatolimab in monotherapy will be guided by a Bayesian Logistic Regression Model (BLRM). The probability that the true Dose Limiting Toxicity (DLT) rate exceeds 50% should be lower than 25% to declare that sabatolimab in monotherapy is reaching an acceptable level of toxicity.
	Efficacy of sabatolimab will be assessed based on the proportion of adult participants treated with sabatolimab at the recommended dose for expansion, as monotherapy or in combination with azacitidine, who remain with no evidence of hematologic relapse after 6 cycles of study treatment as per investigator assessment and using a Bayesian dual-criterion design: Adult participants treated with sabatolimab monotherapy: At least 8 participants with no evidence of hematologic relapse after 6 cycles of treatment out of 25 participants are required for success
	 Statistical decision rule: the posterior probability that the proportion of adult participants who remain with no evidence of hematologic relapse after 6 cycles of study treatment ≥ 15% is at least 97.5% (statistical significance at 2.5% level, 1-sided) Clinical decision rule: the posterior median for the proportion of adult participants who remain with no evidence of hematologic relapse is ≥ 30%.

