4.5 Purpose and timing of interim analyses/design adaptations

Interim analyses are planned for the monitoring of safety data (see Section 12.7).

The study design foresees that during and at the conclusion of Part 1 (Safety Run-in), decisions based on emerging data are made at safety review meetings following completion of enrollment at each dose level (or earlier if required) and prior to starting Part 2. The decision to escalate to the 800 mg Q4W dose level in Part 1 and the selection of the preferred

dose level for Part 2, will be based, principally, on the occurrence of dose limiting toxicities (DLTs) (see Table 6-2). The decision to open the combination cohort (cohort 3), the expansion monotherapy cohort (cohort 4) and the adolescent cohort (cohort 5) will be based on an overall assessment of all available data, including safety, preliminary response assessment, clinical pharmacology, tolerability, and recommendations from participating investigators. All the decisions will be guided by a Bayesian Logistic Regression Model (BLRM) to assess the relationship between the dose of MBG453 and the incidence of DLTs. If the probability that the true Dose Limiting Toxicity (DLT) rate exceeds 50% is less than 25%, the BLRM will recommend pursuing the recruitment and open a new cohort (see Section 6.5.2 for details on guidelines for determination of the recommended dose for expansion). These decisions will be communicated to investigators.

Details of this procedure and the process for communication with investigators are provided in Section 6.5.1 and Section 6.5.2.

The primary efficacy analysis will be performed after all participants of cohorts 3 and 4 have completed at least 6 cycles of study treatment or have been followed for at least 6 months after the first dose of study treatment or have discontinued from the study earlier. See Section 12.7.

Throughout the study, the decision whether or when to open an additional cohort(s) will be based on the overall safety, PK, tolerability, and preliminary response assessment.

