Dose escalation/expansion decisions will be made by Investigators and Novartis study personnel (including the study physician and statistician) during a dose decision meeting by teleconference. Decisions will be based on a synthesis of all relevant data available from all dose levels evaluated in the ongoing study including safety information, incidence and severity of aGvHD and cGvHD, incidence of DLTs, all Common Terminology Criteria for Adverse Events (CTCAE) Grade ≥ 2 toxicity data during the first two cycles, available PK and PD data from evaluable participants.

The recommended dose for the next cohort of participants (second cohort in the safety runin part, expansion cohort, combination cohort and adolescent cohort) will be guided by a Bayesian logistic regression model (BLRM) and by applying the following principle: the risk to have $\geq 50\%$ DLTs including GvHD must be below 25%. This adaptive Bayesian methodology has the advantage to incorporate information gained at the preceding dose levels. Thus, additional participants may be enrolled at this dose level or a higher dose level as agreed by Investigators and Novartis personnel and if the BLRM predicts that the risk to have $\geq 50\%$ dose limiting toxicities (DLTs) including GvHD remains below 25%.

Sabatolimab administration at the next higher dose level (sabatolimab 800 mg Q4W) or starting the recruitment of the Part 2 of the study (monotherapy expansion cohort, combination cohort and adolescent cohort) may not proceed until the investigator receives written confirmation from Novartis indicating that the results of the previous cohort were evaluated and that it is permissible to proceed to open a new cohort.

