12.4.2 Statistical model, hypothesis, and method of analysis

Primary safety analysis in adults (incidence of treatment-emergent dose-limiting toxicities including but not limited to GvHD)

Assessing whether sabatolimab at the tested dose levels does not lead to an unacceptable level of toxicity (DLTs) in adults will be guided by a Bayesian Logistic Regression Model (BLRM). This single-agent model will assess the relationship between the log-dose of sabatolimab and

the incidence of dose-limiting toxicities (DLTs). Details about this model is provided in Section 16.6.

The posterior probability that the true incidence of dose-limiting toxicity (DLT) including aGvHD and cGvHD is lower than 50% will be summarized after each cohort in the safety runin part. If this posterior probability is less than 25%, it would be recommended to start the next cohort.

Primary safety analysis in adolescents (incidence of treatment-emergent dose-limiting toxicities including but not limited to GvHD)

Assessing whether sabatolimab at the recommended dose for adults does not lead to an unacceptable level of toxicity (DLTs) in adolescents will be guided by the same Bayesian Logistic Regression Model (BLRM) than used for the adult cohorts of the safety run-in part. Details about this model is provided in Section 16.6.

The posterior probability that the true incidence of dose-limiting toxicity (DLT) is lower than 50% will be summarized for the adolescent cohort.

Primary efficacy analysis (proportion of adult participants with no evidence of hematologic relapse)

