16.6 Appendix 6: Statistical details on the Bayesian Logistic Regression Model (BLRM)

Statistical Models

The safety run-in part of this study to confirm that the sabatolimab is safe will be guided by a Bayesian analysis of dose limiting toxicity (DLT) data. The statistical model will be a Bayesian Logistic Regression Model (BLRM) consisting of a single agent dose-DLT component.

Let π (d) be the risk of DLT for sabatolimab given as a single agent Q4W at dose d. The single agent dose-DLT model is as follow:

 $logit(\pi(d)) = log(\alpha) + \beta log(d/d^*)$

where d*= 800 mg Q4W (reference dose of sabatolimab) is used to scale the doses of sabatolimab. Hence, α (>0) is the single-agent odd of a DLT at 800 mg Q4W; β (>0) is the increase in the log-odds of a DLT by a unit increase in log-dose.

Taking into account the intrinsic risk of GvHD (which is part of the DLT definition) in the posttransplant setting, we selected a weakly informative prior with means corresponding to a risk of DLT at the reference dose of 15%, and a doubling in dose leading to a doubling in the odds of the risk of a DLT.

No meta-analytic-predictive (MAP) approach was used to derive the prior distribution as historical data are not available in this post-transplant setting.

The prior distribution is specified in Table 16-9.

Table 16-9 Prior distribution

Parameter	Prior distribution		
μ1	N(mean = logit(0.15), sd = 2)		
μ2	N(mean = 0, sd=1)		

The recommended dose for expansion will be the highest dose between 400 mg and 800 mg Q4W for which the probability of excessive toxicity (i.e. DLT rate $\geq 50\%$) is less than 0.25.

The summary of prior distribution of DLT rates is specified in Table 16-10.

Summary of prior distribution of DLT rates **Table 16-10**

Dose of sabatoli mab	Prior probabilities that P(DLT) is in the interval: [0, 0.50) [0.50,1]		Mean	SD	Quantiles	;			
					2.5%	50%	97.5%		
400 mg Q4W	0.897	0.103	0.163	0.220	0.000	0.061	0.813		
800 mg Q4W	0.806	0.194	0.257	0.264	0.003	0.151	0.900		

Hypothetical on-study scenarios

To illustrate the performance of the BLRM used to guide the tolerability assessment in the safety run-in part for sabatolimab in monotherapy, hypothetical data scenarios are displayed in Table 16-11. Decision will be based on additional safety, PK or PD information.

Table 16-11 Probability of unacceptable toxicity for different hypothetical scenarios

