2.5.2 Statistical hypothesis, model, and method of analysis

Primary safety analysis in adults (safety run-in part only)

A Bayesian model will be used to assess whether sabatolimab at the two tested dose levels is not meeting an unacceptable level of toxicity in adults from the DDS. The threshold to qualify for an acceptable level of toxicity was higher (50%) than the standard threshold used in phase I study (33%) because:

- aGvHD and cGvHD are included in the DLT definition,
- Yet, the curative efficacy of aHSCT is attributable to GvL, which inherently maybe associated with risk of GvHD,
- Therefore, post-aHSCT immunomodulatory interventions, including sabatolimab, that promote GvL could potentially induce GvHD and other immune-related adverse events.

The relationship between the dose of sabatolimab and the probability of DLT is modeled using a logistic regression detailed in Appendix Section 16.6 of the protocol. A summary of the characteristics of this Bayesian model is presented below:

- A single agent dose-DLT logistic model will assess the toxicity risk of sabatolimab.
- Taking into account the lack of historical data and the intrinsic risk of GvHD (which is part of the DLT definition) in the post-aHSCT setting, a weakly informative priors with means corresponding to a risk of DLT at the reference dose of 15%, and a doubling in dose leading to a doubling in the odds of the risk of a DLT were selected.

Novartis	Confidential	Page 22 of 35
SAP – Amendment 1		CMBG453F12201

• The prior risk of excessive toxicity (i.e. risk of DLT within [50%-100%]) is 10.3% for the sabatolimab 400 mg Q4W and 19.4% for the sabatolimab 800 mg Q4W.

After each cohort in the safety run-in part, the posterior distribution for the risk of DLT for new participants at the dose level of interest will be evaluated. The posterior distributions will be summarized to provide the posterior probability that the risk of DLT for each dose level of sabatolimab lies within the interval [50%, 100%] (i.e. excessive toxicity). After the first cohort, if this posterior probability is less than 25% for the two dose levels (400 mg and 800 mg), it would be recommended to start enrolling participants in Cohort 2 with sabatolimab 800 mg Q4W dose level.

Primary safety analysis in adolescent (Cohort 5 only) - Not assessable

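### Protocol Section 12.4.2 states the Bayesian toxicity go rule backwards: safe data block the next cohort and highly toxic data open it

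*Protocol*

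**What the plan says.** In the adult safety paragraph of Protocol Section 12.4.2 two sentences follow one another. The first names the quantity: "The posterior probability that the true incidence of dose-limiting toxicity (DLT) including aGvHD and cGvHD is lower than 50% will be summarized" after each run-in cohort. The second sets the rule: "If this posterior probability is less than 25%, it would be recommended to start the next cohort". The adolescent paragraph reports the same below-50% probability but attaches no decision to it.

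Elsewhere the rule uses the other tail:

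- Protocol summary, data analysis: "The probability that the true Dose Limiting Toxicity (DLT) rate exceeds 50% should be lower than 25"%.
- Section 4.5: "If the probability that the true Dose Limiting Toxicity (DLT) rate exceeds 50% is less than 25%, the BLRM will recommend pursuing the recruitment".
- Section 6.5.2: the risk of at least 50% "DLTs including GvHD must be below 25"%.
- Section 12.8.1 and the footnote to Table 12-1: acceptable toxicity means a probability of excessive toxicity under 0.25.
- Section 16.6: "The recommended dose for expansion will be the highest dose between 400 mg and 800 mg Q4W for which the probability of excessive toxicity" (a DLT rate of at least 50%) is under 0.25.
- SAP Section 2.5.2 summarises the probability that the DLT risk lies between 50% and 100%, then continues: "After the first cohort, if this posterior probability is less than 25% for the two dose levels (400 mg and 800 mg"), enrolment in Cohort 2 is recommended.

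SAP Section 4, which lists changes to protocol-specified analyses, reads as not applicable.

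**The concern.** In Section 12.4.2 the demonstrative in the decision sentence can refer only to the below-50% probability in the sentence before it. A small value of that probability means the dose is probably too toxic, yet the text makes it the condition for going on.

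Section 12.4.2 is the protocol's statistical method for the first primary objective. It covers escalation in a setting where, by the protocol's own account, no sabatolimab safety data exist. Section 10.2 provides no independent safety committee, so the sponsor and investigators decide. They should not hold two formal go rules that contradict each other.

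**Working it through.** **Logic.** Let π be the true DLT rate at the dose in question.

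- Intended rule: go if P(π ≥ 0.5) < 0.25, which is the same as P(π < 0.5) > 0.75.
- Section 12.4.2 as written: go if P(π < 0.5) < 0.25, which is the same as P(π ≥ 0.5) > 0.75.

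At a given dose the two conditions can never both hold. (Whether the limit is written as exceeding 50% or as at least 50% makes no difference, because the posterior is continuous.)

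**Inputs (Section 16.6).** The model is logit π(d) = log α + β·log(d/800), so logit π(800) = log α and logit π(400) = log α + β·log(0.5). Table 16-9 labels its two parameters μ1 and μ2; I take them as log α ~ N(logit 0.15, SD 2) and log β ~ N(0, SD 1). This fits the description in the text: the 800 mg prior is centred at 15%, and β = 1 gives 2^1 = 2, a doubling of the odds when the dose doubles. The likelihood is binomial and the posterior is obtained by numerical integration on a grid.

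**Reproducing the plan's figures.** The prior P(π ≥ 0.5) comes out at 0.103 for 400 mg and 0.194 for 800 mg, as in Table 16-10 and SAP Section 2.5.2. Taking the highest dose with P(π > 0.5) < 0.25 reproduces all 14 decisions in the 50% columns of Table 12-1, with probabilities within about 0.006. Examples: 1/6 gives 800 mg with 0.131 (stated 0.125); 2/8 gives 800 mg with 0.221 (stated 0.216); 2/8 then 4/9 gives 800 mg with 0.226 (stated 0.224); 3/6 gives stop.

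**Applying both rules after Cohort 1 (6 evaluable participants at 400 mg).**

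| DLTs | P(π<0.5), 400 mg | P(π<0.5), 800 mg | P(π≥0.5), 800 mg | Open 800 mg: intended rule | Open 800 mg: Section 12.4.2 as written |
|---|---|---|---|---|---|
| 0/6 | 0.999 | 0.965 | 0.035 | yes | no |
| 1/6 | 0.986 | 0.869 | 0.131 | yes | no |
| 2/6 | 0.902 | 0.662 | 0.338 | no | no |
| 3/6 | 0.681 | 0.390 | 0.610 | no | no |
| 4/6 | 0.371 | 0.161 | 0.839 | no | yes |
| 5/6 | 0.127 | 0.042 | 0.958 | no | yes |
| 6/6 | 0.022 | 0.006 | 0.994 | no | yes |

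Judged on the 800 mg value, the rules disagree in five of the seven possible outcomes: the two safest and the three most toxic. Section 12.4.2 does not name the dose. If the written condition had to hold at both doses, as the SAP rule does, 4/6 would no longer open the cohort (0.371 at 400 mg), but 5/6 and 6/6 still would. With 8 participants, 0/8 to 4/8 would not open 800 mg under the written rule, while 5/8 would (0.155 at 800 mg).

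**Table 12-1 under the written rule.** Nine of the 14 scenarios recommend 800 mg at the 50% limit. Among these the smallest P(π < 0.5) at 800 mg is 0.774 (2/8 then 4/9), far above 0.25. In the other five it is 0.662 (2/6), 0.390 (3/6), 0.574 (3/8), 0.681 (0/6 then 5/9) and 0.622 (1/6 then 5/9). None of the 14 would open the next cohort.

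**The case against.** The strongest reply is that this is a slip of one phrase which the rest of the documents correct. The right rule appears in at least six other places. Section 12.4.2 itself sends the reader to Section 16.6, where the rule is stated correctly. Section 12.7 points to Section 6.5.2 for dose decisions, and the SAP specifies the correct tail. The model only guides: investigators and the sponsor weigh all safety, PK and PD data, and written sponsor confirmation is needed before a cohort opens. A cohort with 5 DLTs in 6 would not lead to 800 mg through that process. The text also never says to stop; it only withholds the recommendation to start. Finally, the programme was ended for non-safety reasons, recruitment was halted in December 2023, and one adolescent had already been enrolled in Part 2, which opens only after the run-in decisions.

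Most of this stands as a limit on consequences. Practical harm was unlikely, and no future cohort decision appears to depend on the sentence. The adolescent paragraph is not inverted: it has no go rule and reports the complement of the SAP quantity, in an analysis the SAP now marks as not assessable. But correct wording elsewhere does not make the written rule right. The SAP departs from Section 12.4.2 without saying so.

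**Conclusion.** The point holds. Section 12.4.2 reverses the go rule for the primary safety objective. As written, no Cohort 1 result from 0/6 to 3/6 opens the next cohort, while 5/6 and 6/6 do whichever dose the probability refers to. The published decision table can be reproduced only with the probability of a DLT rate above 50% kept under 25%.

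The numbers rest on reading μ1 and μ2 as log α and log β, which the match to Tables 16-10 and 12-1 supports. The direction of the error needs no model; it follows from the two sentences. It is a wording error confined to Section 12.4.2, but because it concerns a primary safety decision rule it should be corrected rather than left to be inferred.

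**What to change.** In the adult paragraph of Section 12.4.2, change the summarised event to a true DLT rate of 50% or higher and keep the 25% limit. (Keeping the below-50% event and requiring more than 75% is equivalent.) Name the dose to which the probability applies, consistent with Section 6.5.2 and SAP Section 2.5.2. Report the same quantity in the adolescent paragraph so that it matches the SAP.

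Since the trial is closing, a clarification letter would do in place of an amendment, together with an entry in SAP Section 4 and a note in the final report stating which rule was applied at each safety review.

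The cost is a sentence or two. Table 12-1, Section 16.6, the sample size and the data are unchanged.

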12.4.3 Handling of intercurrent events of primary estimand

Handling of remaining intercurrent events of the primary efficacy and safety estimands are described in Section 2.1.

12.4.4 Handling of missing values not related to intercurrent event

For the determination of the absence of evidence of hematologic relapse (ie, no evidence of bone marrow blasts ≥5%; no evidence of reappearance of blasts in the blood; no evidence of development of extramedullary disease) after 6 cycles of treatment, only the response assessment performed at Cycle 7 Day 1 or the response assessment performed 6 months after starting the study treatment is considered.

An adequate response assessment is considered any disease assessment indicating response status apart from "unknown" or "not done". Evaluation of response relies on bone marrow, peripheral blood, and extramedullary disease assessment. In case of missing data for the full assessment required to qualify for a given response or in case of a more than 7 days difference between bone marrow aspirate/biopsy assessments and hematology assessments of the same visit, the overall assessment "unknown" was assigned unless relapse was seen in at least one compartment (i.e. bone marrow or blood).

A participant will be considered with no evidence of hematologic relapse if an adequate response assessment indicates a complete remission (CR) or a complete remission with incomplete hematologic recovery (CRi) response; and even if one or several inadequate response assessments ("unknown" or "not done") have been documented prior to the current adequate response assessment.

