8.3 Efficacy

8.3.1 Efficacy response assessment

Response assessments (bone marrow aspirate (BMA)/bone marrow biopsies (BMB)), peripheral blood, hematology assessments, extramedullary disease assessments) will be performed locally, by the Investigator, according to the assessment schedule depicted in Table 8-1 and Table 8-2 for assessment of relapse; complete remission, or complete remission with incomplete hematologic recovery.

Bone marrow assessments will be performed at screening, and pre-dose on C2D1, C3D1, C4D1 and C7D1 and every 3 cycles D1 until Cycle 13 D1 and then every 6 months and as clinically indicated until relapse, start of a new anti-neoplastic treatment, death, lost to follow-up or withdrawal of consent.

For sabatolimab monotherapy cohort participants, hematology assessments will be performed at screening, and pre-dose on D1 and D15 for the two first cycles and thereafter at D1 of each

cycle, at the end of treatment visit, at unscheduled visit as clinically indicated, and every 12 weeks for participants who enter post-treatment follow-up.

For sabatolimab in combination with azacitidine cohort participants, hematology assessments will be performed at screening, and pre-dose on D1, D5 and D15 for the two first cycles and thereafter on D1 and D5 of each cycle, at the end of treatment visit, at unscheduled visit as clinically indicated, and every 12 weeks for participants who enter post-treatment follow-up.

Response evaluation will be based on the Investigator's assessment based on standardized criteria as proposed by the International Working Group (IWG) and European Leukemia Network (ELN) for AML (Cheson et al 2003, Döhner et al 2017) (see Table 8-1 and Table 8-2). Disease classification at baseline and evaluation of response during study treatment will rely on bone marrow, peripheral blood assessment, as well as the presence or absence of extramedullary disease. For disease characterization at baseline, the last assessment of bone marrow (within 28 days before study treatment starts) and peripheral blood counts (within 14 days before study treatment starts) at the screening visit should be used. In case of missing data for the full assessment required to qualify for a given response, the overall assessment "unknown" will be assigned unless relapse was seen in at least one compartment (i.e. bone marrow or blood, or appearance of extramedullary disease).

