incomplete hematologic	Peripheral blood: No circulating blasts or blasts with Auer rods		
recovery (CRi)	No evidence of extramedullary disease (such as CNS or soft tissue involvement)		
	Neutrophils < 1.0x10 ⁹ /L or platelets < 100x10 ⁹ /L		
Hematologic relapse	Only in participants with CR or CRi. Any of the following:		
(from CR or CRi)	Reappearance of blasts in peripheral blood		
	OR		
	Bone marrow blasts ≥ 5%		
	OR		
	Development of extramedullary disease		
Unknown	In case the response assessment was not done, or the assessment was incomplete		

¹ If not defined otherwise, all of these criteria apply

Post treatment efficacy follow up

Participants who discontinue treatment for reasons other than documented relapse from CR/CRi, death, lost to follow-up, or withdrawal of consent, will enter the post-treatment follow-up phase (Section 9.2). Hematology assessments must continue to be performed every 3 months, response should be assessed at least every 6 months, and bone marrow assessment should be done at least every 6 months until relapse or start of new therapy per Table 8-1 and Table 8-2, or as clinically indicated any time in case relapse is suspected.

The post-treatment follow-up period will last until participant's documented relapse (per ELN criteria (Döhner et al 2017), see Table 8-1 and Table 8-2, start of new therapy, death, lost to follow-up, or withdrawal of consent or the end of study whichever comes first.

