12.4.1 Definition of primary endpoint(s)

For the primary safety objectives (for adults and adolescents separately), the primary variable is the proportion of participants from the DDS who reported a dose-limiting toxicity (DLT) (see Section 6.5.3 for details) during the first two cycles.

For the primary efficacy objective, the primary variable is the proportion of adults from the FAS treated at the recommended dose for expansion (RDE) who report no evidence of hematologic relapse (no evidence of bone marrow blasts ≥5%; no evidence of reappearance of blasts in the blood; no evidence of development of extramedullary disease) as per investigator assessment (Table 8-3) after 6 cycles of study treatment.

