- 3. Treatment of interest: Treatment with sabatolimab or sabatolimab in combination with azacitidine taken for the entire study duration post aHSCT. One estimand for each of the two treatments of interest (sabatolimab in monotherapy and sabatolimab in combination with azacitidine) will be considered.
- 4. Handling of intercurrent events:

- Failure to complete 6 cycles of treatment due to death for any reason or relapse: a participant who dies or has a relapse before completing 6 cycles of treatment will be considered as a non-responder (composite variable strategy).
- Start of donor lymphocyte infusions (DLI) or a new anti-neoplastic therapy before completing 6 cycles of study treatment: a participant who starts a DLI or a new antineoplastic therapy before completing 6 cycles of treatment will be considered as a non-responder (composite variable strategy).
- Failure to complete 6 cycles of treatment due to reasons other than relapse and death for any reason (including due to adverse events, graft vs. host disease for example): all participants with an adequate response assessment (other than "unknown" response) will be taken into account regardless of any study treatment interruption or permanent discontinuation; for a participant who stops the study due to reasons other than relapse or death, we will ask the participant to perform a response assessment 6 months after starting study treatment; a participant with no evidence of hematologic relapse 6 months after starting treatment will be considered a responder (treatment policy strategy).
- 5. Summary measure for the primary efficacy estimand is the proportion of participants with no evidence of hematologic relapse with its exact 95% confidence interval for each of the two study treatment of interest: sabatolimab in monotherapy and sabatolimab in combination with azacitidine. The trial will be successful if at least one of the treatments of interest (sabatolimab monotherapy or sabatolimab in combination with azacitidine) meets both statistical and clinical significance.

The **primary safety estimand for adolescent participants** included in this study is described by the following attributes:

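### Protocol 12.4.4 omits extramedullary disease from the rule that stops an incomplete assessment being coded unknown, although 8.3.1, Table 8-3 and the endpoint definition count it as relapse

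*Protocol*

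**What the plan says.** The rule for incomplete response assessments appears twice in the protocol, with different endings.

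- **Protocol 8.3.1** (how response is assessed): missing data lead to *unknown* "unless relapse was seen in at least one compartment (i.e. bone marrow or blood, or appearance of extramedullary disease".
- **Protocol 12.4.4** (how the primary endpoint is derived when data are missing): missing data, or a gap of more than 7 days between marrow and hematology at the same visit, lead to *unknown* "unless relapse was seen in at least one compartment (i.e. bone marrow or blood". The list stops there.

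The surrounding text treats extramedullary disease as one of three compartments. Table 8-3 lists "Development of extramedullary disease" as sufficient for hematologic relapse on its own. Section 12.4.1 defines the endpoint to include "no evidence of development of extramedullary disease) as per investigator assessment (Table 8-3) after 6 cycles of study treatment". Section 12.4.4 itself, just before the rule, states: "Evaluation of response relies on bone marrow, peripheral blood, and extramedullary disease assessment". The *unknown* row of Table 8-3 reads "In case the response assessment was not done, or the assessment was incomplete" and carries no exception for relapse.

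The SAP does not restate the compartment rule. It refers to Table 8-3 for the response categories (2.5.1) and then says how an *unknown* at Cycle 7 Day 1 or 6 months is resolved (2.5.4).

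**The concern.** The exception in 12.4.4 is introduced by *i.e.*, so it reads as a complete list. Consider a participant with documented extramedullary disease at the deciding assessment whose marrow was not done, or was taken more than 7 days from the blood count. Section 8.3.1 calls this relapse; 12.4.4, taken literally, calls it unknown. Section 12.4.4 also widens the way in, because 8.3.1 does not make mistiming a cause of *unknown*.

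At stake is whether one of the three components of the primary endpoint can be lost in derivation. SAP 2.5.4 resolves an *unknown* by the subsequent assessment, so a relapse coded that way could in principle end as a response. No sensitivity analysis is planned that would show it (Protocol 12.4.5, SAP 2.5.5).

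**Working it through.** **1. Where the literal rule leads.** The case is extramedullary relapse with marrow or blood missing, or the two more than 7 days apart.

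| Situation | Rule that applies | Result |
|---|---|---|
| Relapse before 6 cycles are completed | Composite strategy, SAP 1.2.1: "a participant who dies or has a relapse before completing 6 cycles of treatment will be considered as a non-responder" | Non-responder |
| At Cycle 7 Day 1 or 6 months, under 8.3.1 | Extramedullary exception applies | Relapse, non-responder |
| Same, under 12.4.4; next assessment missing or unknown | SAP 2.5.4, third bullet | Non-responder |
| Same, under 12.4.4; next assessment shows relapse | SAP 2.5.4, second bullet | Non-responder |
| Same, under 12.4.4; next assessment shows CR or CRi | SAP 2.5.4, first bullet | Responder |

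Only the last row differs from the intended result. The rule that makes a participant who starts DLI or new antineoplastic therapy a non-responder covers starts before 6 cycles are completed, so it does not close this row when the disease is found at Cycle 7 Day 1.

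**2. How likely the last row is.** Treatment beyond relapse is not permitted (Protocol 6.1.5.1), and efficacy follow-up ends at relapse or new therapy (6.2.2, 8.3.1, 9.1.1.2). A participant whom the investigator judges to have relapsed has no further scheduled response assessment, so the third row is the more likely end point.

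**3. Relapse-free survival.** Protocol 12.5.1 and SAP 2.6.1 run RFS to the first documented hematologic relapse or death. Neither repeats the 12.4.4 parenthesis. If the coding were carried over, the relapse would not be an event on its date. If new therapy or DLI followed, the participant would be censored at the last adequate assessment before it.

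**4. Decision boundaries.** Inputs are a Beta(1,1) prior and success at 8 or more of 25 (monotherapy) or 11 or more of 20 (combination), from Protocol 12.8.1. The plan's figures reproduce:

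- P(X ≥ 8 | n = 25, p) = 2.55% at p = 0.15 (stated 2.5%), 69.4% at 0.35 and 84.6% at 0.40 (both as stated).
- P(X ≥ 11 | n = 20, p) = 1.71% at p = 0.30 (stated 1.7%) and 75.5% at 0.60 (as stated).
- From the posterior Beta(1 + r, 1 + n − r), the probability that the monotherapy rate is at least 15% is 0.968 at 7/25 (fails) and 0.989 at 8/25 (succeeds). The probability that the combination rate is at least 30% is 0.974 at 10/20 (fails) and 0.991 at 11/20 (succeeds).

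One participant moves the estimate by 1/25 = 4 points or 1/20 = 5 points.

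**5. Illustration under an assumption.** The documents give no rate for the last row of the table. Suppose a proportion x of all participants were wrongly counted as responders, so that the null rate becomes p₀ + x:

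| x (assumed) | P(X ≥ 8 of 25), p = 0.15 + x | P(X ≥ 11 of 20), p = 0.30 + x |
|---|---|---|
| 0 | 2.55% | 1.71% |
| 1% | 3.6% | 2.2% |
| 2% | 5.0% | 2.8% |
| 4% | 8.6% | 4.3% |

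Here x is a joint proportion: extramedullary relapse at the deciding visit, an otherwise incomplete or mistimed assessment, and a later CR or CRi.

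**The case against.** The strongest reply is that this is a drafting slip which the rest of the plan already settles. The endpoint is investigator-assessed against Table 8-3, where extramedullary disease alone is relapse. The SAP takes its response categories from that table and never repeats the narrower list. At Cycle 7 Day 1, marrow, blood and extramedullary assessments are scheduled together, and an unscheduled visit without a marrow is not the assessment that 12.4.4 classifies. The responder bullet in SAP 2.5.4 speaks of CR or CRi being maintained, and a remission regained through new therapy after extramedullary disease is hard to describe that way. SAP 2.6 also provides a listing of all response assessments by participant, so a case could be seen.

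Most of this stands as a limit on the consequence. It does not remove the inconsistency: 12.4.4 is the protocol's stated derivation rule for the primary endpoint, and SAP Section 4 records no change to the protocol-specified analyses. The result should not depend on which section a programmer follows.

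The one-participant boundary is arithmetically right but generic, since any rule based on a count has one. It also carries less weight now: the SAP reports that recruitment was halted, that the study is ending early, and that the p-value will not be assessed.

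**Conclusion.** The inconsistency is real, and 12.4.4 is wrong as written against 8.3.1, Table 8-3 and the endpoint definition. Its reach is narrow. For the primary endpoint a wrong result needs extramedullary relapse at Cycle 7 Day 1 or 6 months, an otherwise incomplete or mistimed assessment, and then a later CR or CRi. Without that last step the participant is a non-responder under either reading. Few participants would be affected, and the size cannot be estimated from the documents; the 1% to 4% range above is an assumption.

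A reader might infer that extramedullary relapses would generally be counted as successes, or would drop out of the RFS curve, so that both analyses are biased in favour of the drug. The documents do not support this. SAP 2.5.4 makes an *unknown* followed by a missing or unknown assessment a non-response, and the plan's follow-up rules make that the likelier course. The RFS definitions rest on documented relapse and do not import the 12.4.4 list, so the RFS effect is conditional on someone applying that list there.

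**What to change.** In Protocol 12.4.4, replace the closing parenthesis of the rule with the 8.3.1 version, so that the exception reads "unless relapse was seen in at least one compartment (i.e. bone marrow or blood, or appearance of extramedullary disease". In SAP 2.5.4 and 2.6.1, add one sentence: relapse documented in any one of the three compartments is relapse on that date, even if another compartment is missing or falls outside the 7-day window. If only the SAP is changed, record the departure from 12.4.4 in SAP Section 4.

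The cost is one phrase in the protocol and one sentence in each of two SAP sections. The success rules of 8/25 and 11/20, the sample sizes and the data collected stay as they are. For the primary endpoint, the correction can only leave the number of responders unchanged or lower it.
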